5.5.5 Permitted dose adjustments and interruptions of study treatment

Study treatment dose adjustments are not permitted during the study. Interruptions are permitted if clinically indicated.

Conditions/events that may lead to the study drug interruptions based on Investigator judgment and overall clinical assessment include:

- reported serious adverse event;
- emergency medical condition, unplanned hospitalization, involving use of excluded concomitant medications;
- abnormal laboratory value(s) or abnormal test or examination result(s)

Should the patient interrupt the study drug for whatever reason, re-start decision should be made on a case-by-case basis (refer also to [Section 5.5.4](#)). Should the Investigator decide,

after informing the Sponsor, to re-initiate treatment with study drug, depending on the duration of the interruption, the first sc at re-start may need to take place at the study site to ensure observation in a similar manner as on Day 1 and Week 24.

The reason for the interruption of treatment and date of interruption should be appropriately documented in the source documents as well as in the appropriate eCRF.

5.5.6 Recommendations for the treatment of MS relapses

MS relapses may be treated with a standard short course of corticosteroids (e.g. methylprednisolone) on an inpatient or outpatient basis. Steroid treatment should consist of 3-5 days and up to 1,000 mg methylprednisolone/day or equivalent. The decision to treat should be based on Investigator's judgment and/or local clinical practice. Standard of care will be followed during treatment.

Taper with oral steroids is not permitted.

Investigators should consider the added immunosuppressive effects of corticosteroid therapy and increase vigilance regarding infections during such treatment and in the weeks following administration.

Use of steroids for treatment of relapse must be recorded on the appropriate eCRF.

5.5.7 Concomitant medication

The Investigator must instruct the patient to notify the study site about any new medications he/she takes after the patient was enrolled into the study. All medications (including dose changes), procedures and significant non-drug therapies (including physical therapy and blood transfusions) administered after the patient was enrolled into the study must be recorded in the appropriate CRF.

Each concomitant drug must be individually assessed against all exclusion criteria/prohibited medication. If in doubt the Investigator should contact the Sponsor before randomizing a patient or allowing a new medication to be started.

Premedication prior to sc injection

Premedication with acetaminophen and/or antihistamines (or equivalent) is recommended and may be administered at the discretion of the Investigator. Only for the first injection of Double-blind treatment period (Day 1) and Double-blind loading dose period (Week 24), the addition of premedication with steroids (methylprednisolone 100 mg iv or equivalent) is recommended. Premedication should be administered 30 to 60 min prior to study drug injection.

Any administration of premedication must be recorded in the appropriate CRF.

Additional information in regards to premedication for home-administration use:

From Week 25 onwards, patients may inject study medication at home (refer to [Section 5.5.4](#)). Use of premedication is at the discretion of the Investigator. Based on the experience with the injections administered at the site and with the use of any premedication, the Investigator will evaluate whether or not premedication (such as acetaminophen and/or antihistamines) should be used before injections administered at home. If premedication is prescribed, the study staff

must ensure that the patient will receive a sufficient supply of premedication for home-use (i.e. to last at least until the next visit) and clear instructions (oral and written) about type and dose of premedication, and when to take it (i.e. 30-60 min before the injection). The Investigator will evaluate the need for premedication, or a change in the prescription, at each visit (planned and unplanned) including at the monthly telephone interview appointments (interview script includes specific questions about any injection-related symptoms and the use of premedication). If, based on the telephone interview, a change in premedication may be needed, the patient should be asked to return to the site for an unplanned visit.

The patients must be comprehensively informed (through the patient information and consent process) about the possibility that injection-related reactions may occur despite use of pre-medications and about the possible symptoms of a systemic injection reaction and their management. The patients will additionally receive an injection instructions leaflet (Instructions for Home administration and Use) which also includes information about such reactions, their management as well as Investigator/site contact numbers. Furthermore, patients must be reminded to always carry their Patient Card which includes the Investigator and site telephone contact numbers in case of an emergency.

5.5.8 Prohibited medication

Use of the treatments displayed in [Table 5-1](#) is NOT allowed in combination with study treatment, due to increased risk of immunosuppression and confounding of efficacy evaluations.

Exclusionary medications for study eligibility are listed in the exclusion criteria ([Section 4.2](#)). Use of excluded medications is not allowed after randomization while the patient is on study medication.

Table 5-1 Prohibited medication

Medication	Additional action to be taken
Immunosuppressive/chemotherapeutic medications (including herbal) or procedures, including but not limited to cyclosporine, azathioprine, methotrexate, cyclophosphamide, mitoxantrone, lymphoid irradiation and hematopoietic stem cell transplantation	Discontinue study treatment, increase vigilance regarding infections. NOTE: Restarting study treatment in patients exposed to these medications is not permitted.
Monoclonal antibodies targeting the immune system, including but not limited to natalizumab, alemtuzumab, daclizumab and B-cell depleting agents such as but not limited to rituximab, ocrelizumab and obinutuzumab	Discontinue study treatment, increase vigilance regarding infections. NOTE: Restarting study treatment after exposure to B-cell depleting agents is not permitted. For others only after consultation with the Sponsor.
Any other immunomodulatory or disease-modifying MS treatment, including but not limited to fingolimod, interferon beta, glatiramer acetate, dimethyl fumarate, intravenous immunoglobulin, plasmapheresis or systemic corticosteroids (except for when given for MS relapse treatment as defined in Section 5.5.6).	Interrupt or discontinue study treatment, increase vigilance regarding infections.

Medication	Additional action to be taken
Leflunomide, teriflumonide	Discontinue study treatment
Administration of any live or live-attenuated vaccine (including for measles) is prohibited while patients are exposed to study drug (long-lasting effects of the study drugs should be taken into consideration)	They may be administered when patients are no longer exposed to study drug. Consider risk/benefit and follow local labels

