5.4 Treatment blinding

This study will be conducted using a double-blind design. Patients will be assigned to receive either active ofatumumab or ofatumumab-matching placebo as described in [Section 5.2](#).

Patients, Investigator staff, persons performing the assessments, and data analysts will remain blinded to the identity of the treatment assignment from the time of randomization until database lock, using the following methods: (1) Randomization data are kept strictly confidential until the time of unblinding, and will not be accessible by anyone involved in the study with the following exceptions: DMC members, Independent Statisticians and Independent Programmers. (2) The identity of the treatments will be concealed by the use of study drugs that are all identical in packaging, labeling, schedule of administration and appearance.

The randomization codes associated with PK samples will be disclosed to the Bioanalysts who will keep PK and Anti-human antibodies (ADA) results confidential until database lock.

The following measures will be taken to protect the blinding of the Independent EDSS Rater (Rater):

- Prohibited access to patients' study data
- Separate binders of worksheets and CRF materials for Investigator and the Rater
- Prohibited cross-over of Investigator and Rater
- Use of appropriate clothing by patients to cover potential injection sites during neurological examinations
- Limited interactions between Rater and patient: permitting only a minimum required to perform the EDSS rating.

Additionally, potentially unblinding laboratory parameters (e.g. B-cell counts) will not be communicated to the Investigator or other study staff as described in [Section 3.1](#) and [Section 6.5.4](#).

Unblinding will only occur in the case of patient emergencies (see [Section 5.5.9](#)) and at the conclusion of the core part.

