If the patient cannot attend any further study visit(s), the site staff should maintain regular telephone contact with the patient, or with a person pre-designated by the patient, unless the patient has withdrawn informed consent (see [Section 5.6.3](#)). This telephone contact should preferably be done according to the study visit schedule.

The Investigator must also contact the IRT to register the patient's discontinuation from study treatment.

If study drug discontinuation occurs because treatment code has been broken, please refer to [Section 5.5.9](#).

Note: Patients who prematurely discontinue study drug and complete their EOS visits will enter the Safety FU period ([Table 6-2](#)) for continued follow-up (See [Section 3.1](#), [Section 5.6.1](#)). The patients should be encouraged to stay in the study and continue to follow the procedures and assessment schedule as specified in the protocol.

The Investigator should consider the benefit/risk of initiation of alternative MS therapy in terms of the patient's clinical status, local regulations, treatment guidelines and local prescribing information. In some cases, as described below, information on the patient's circulating B-cell status may be requested if in the Investigator's opinion this is needed to ensure safe switch to another MS therapy.

The duration of the washout period after last dose of study drug will depend on the type of therapy to be initiated and the patient's clinical status:

- A washout period of at least 5 months is recommended before initiation of lymphocyte depleting/suppressing/trafficking blocking agents (e.g. alemtuzumab, fingolimod, natalizumab, teriflunomide, etc.). This is in line with the expected circulating B-cell repletion course after ofatumumab discontinuation (estimated around 5 months needed for 80% repletion; see [Section 3.3](#))
- If, in the opinion of the Investigator, the safe initiation of another therapy cannot be considered without the patient's B-cell status, the Investigator must submit a request to Novartis in writing. The request of B-cell status must be justified based on clinical grounds. The Investigator must ensure data entry is complete for any such patients. The Investigator will be notified of whether or not the patient has B-cell counts at or above lower limit of normal or baseline values, whichever is lower. The detailed procedure for requesting and receiving the information on a patient's B-cell status will be provided separately.

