6.5.4 Laboratory evaluations

A central laboratory will be used for analysis of all specimens collected. Details on the collections, shipment of samples and reporting of results by the central laboratory are provided to Investigators in the laboratory manual. Abnormal laboratory parameters, inconsistent with clinical presentation of MS or which cause suspicion of an underlying medical condition, should be repeated for confirmation.

Parameters that may lead to unblinding to treatment assignment such as B-cell and T-cell counts will be blinded to the Investigator and Sponsor study team (e.g. will not be included on the routine safety lab reports sent to the Investigators by the central laboratory). This information will remain blinded during the Core part of this study until the treatment code for the study has been broken.

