6.5.4.1 Hematology

Blood samples will be collected at the planned visits indicated in [Table 6-1](#) and [Table 6-2](#). The parameters assessed will include: red blood cell (RBC) count, hemoglobin, hematocrit, platelets, total WBC count, WBC differential counts (neutrophils, lymphocytes, basophils, eosinophils, monocytes), CD19⁺ B-cell counts and CD3⁺CD20⁺ T-cell counts.

For study blinding purposes, the B-cell and T-cell counts will not be provided to the Investigators and Sponsor study team. B-cell and T-cell counts will be assessed by personnel not otherwise involved in the study for the purpose of determining if continued follow-up is required ([Section 3.1](#)).

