15.3 Guidance on immunization

The safety of and ability to generate a primary or anamnestic response to immunization with live, live-attenuated or inactivated vaccines during ofatumumab treatment has not been investigated. The response to vaccination could be impaired due to B-cells depletion.

It is recommended that the Investigator review the patient's immunization history as part of the initial Screening procedure for a patient being considered for treatment with ofatumumab. Vaccination of the patient, in compliance with local area vaccination guidelines for the patient population being treated, is recommended prior to administration of ofatumumab. In particular, prior to administration of ofatumumab, hepatitis B vaccination, in patients with risk factors for hepatitis B infection or in areas with a high prevalence of hepatitis B, as per local area treatment guidelines should be considered.

Administration of live or live-attenuated vaccines must be avoided during and after treatment with ofatumumab and until B-cell counts are normalized.

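### Protocol Table 5-1 and section 15.3 end the live-vaccine prohibition at different, undefined points, and no route is stated by which B-cell normalization reaches the investigator for a vaccination decision

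*Protocol*

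**What the plan says.** Two places in the protocol state when the live-vaccine prohibition ends.

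- **Table 5-1 (5.5.8 Prohibited medication).** The medication column says that giving such a vaccine "is prohibited while patients are exposed to study drug (long-lasting effects of the study drugs should be taken into consideration". The action column of the same row adds: "They may be administered when patients are no longer exposed to study drug. Consider risk/benefit and follow local labels".
- **Section 15.3 (Appendix 3, Guidance on immunization).** "Administration of live or live-attenuated vaccines must be avoided during and after treatment with ofatumumab and until B-cell counts are normalized".

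Four other places govern what the site can know about B-cells.

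- **6.5.4.1 Hematology** withholds the results: "For study blinding purposes, the B-cell and T-cell counts will not be provided to the Investigators and Sponsor study team".
- **6.5.4 and 5.4** limit that in time. Section 6.5.4 says: "This information will remain blinded during the Core part of this study until the treatment code for the study has been broken". Section 5.4 allows unblinding in patient emergencies "and at the conclusion of the core part".
- **3.1.3 Safety FU period** tells the site only whether follow-up has to go on. That depends on whether B-cells have returned to baseline or to the lower limit of normal by 36 weeks. Patients who began another disease-modifying or immunosuppressive therapy before then are not followed past 36 weeks.
- **5.6.2 Discontinuation of study treatment** lets the investigator ask in writing for a yes/no B-cell status where, in the investigator's opinion, "this is needed to ensure safe switch to another MS therapy".

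**The concern.** A prohibition with two end-points is not one rule. Table 5-1 ties the end to exposure and then leaves the matter to judgement and local labelling. Section 15.3 ties it to a laboratory state and is mandatory. A site that consults only the prohibited-medication table, which is where it would normally look, may reach a different answer from a site that reads the appendix.

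What is at stake is patient safety. The affected patient has received ofatumumab, has stopped it, still has depleted B-cells, and is being considered for a live vaccine. If the section 15.3 condition is the one intended, the protocol should also let the investigator find out whether it has been met, and it does not say how.

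**Working it through.** The point rests on no sample size, power or event figure, so the check is a comparison of the texts.

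**Step 1. The two end-points side by side.**

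| | Table 5-1 | Section 15.3 |
|---|---|---|
| Prohibition ends when | exposure has ended | B-cells have normalized |
| Force after stopping drug | permissive, subject to judgement | mandatory avoidance |
| Is the key term defined? | no definition of *exposed* | no definition of *normalized* |
| B-cell criterion? | none stated | yes, without a threshold |
| Refers to the other text? | no | no |

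**Step 2. Can the two give different answers for the same patient?** They agree only if exposure is taken to last until B-cells normalize. Nothing in Table 5-1 says so. Protocol 3.3 predicts about 5 months to reach 80% repletion after stopping, and repletion in the great majority of patients within 9 months, so depletion outlasts the last dose by months. On any reading in which exposure ends before repletion, a patient in between is eligible for vaccination under Table 5-1, subject to judgement, and ineligible under 15.3.

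**Step 3. Is *normalized* fixed elsewhere?** Sections 3.1.3 and 5.6.2 both use a return to the lower of the patient's own baseline and the lower limit of normal. Section 15.3 cites neither. A patient whose baseline lay below the normal limit could meet that criterion without having counts in the normal range, so the term cannot be carried across without a statement.

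**Step 4. How does the investigator learn that the 15.3 condition is met?**

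- *Counts.* They are withheld under 6.5.4.1. Section 6.5.4 limits this to the Core part until the code is broken, but 6.5.4.1 and 3.1.3 do not repeat that limit, and no section says that counts are sent to sites afterwards. A patient who stops during the Core part can be in Safety FU before the code is broken.
- *Notice under 3.1.3.* Repletion is judged at 36 weeks. A message that follow-up is over means repletion for most patients. It does not for those who started another therapy earlier, because their monitoring stops at 36 weeks whatever the counts.
- *Request under 5.6.2.* This yields the right kind of answer before 36 weeks, but it is framed around changing MS therapy and does not mention vaccination.
- *Contact with the sponsor under 5.5.7.* An investigator in doubt about a new medication is told to ask the sponsor. Under 6.5.4.1 the sponsor study team does not receive the counts either.

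Each route gives part of the information. None is stated to serve a vaccination decision.

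**The case against.** The best defence is that the texts can be read together. The Table 5-1 row itself points to lasting drug effects, and protocol 3.2 uses similar language for the effect on B-cells when it justifies follow-up until repletion. On that view Table 5-1 is the general statement and 15.3 the specific one. This softens the conflict and deserves weight. It does not remove it: a remark that something should be considered is not an end-point, and the row sends the reader neither to 15.3 nor to any B-cell criterion.

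Three stronger readings are tempting, and the documents do not support them.

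- *That the 15.3 rule cannot be applied at the site.* It can. An investigator who does not know the B-cell status complies by withholding the vaccine. The blinding is limited in time under 6.5.4 and 5.4. The Core analysis follows the last patient's Week 28 (section 9), while the Extension runs until the last patient has had 24 weeks in it (3.3), so for completers who do not enter the umbrella study the blinding argument largely falls away. Sections 3.1.3, 5.6.2 and 5.5.7 give partial routes as well. What remains is the narrower gap in step 4.
- *That the gap between the rules can be put in months.* A reader might take the SAP's 100-day safety cut-off as the end of exposure (100 / 30.4 = 3.3 months) and subtract it from 5 and 9 months, giving 1.7 to 5.7 months. The 100 days is a window for reporting safety data, not a definition of exposure in Table 5-1, and 80% repletion is not normalization.
- *That every patient who discontinues is affected.* Patients who stop in the Core part having received only placebo have no drug-induced depletion.

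**Conclusion.** The inconsistency is real and should be corrected. Table 5-1 and section 15.3 end the same prohibition at different points, in undefined terms and without cross-reference. The conclusion assumes only that *exposed* does not already mean *until B-cells normalize*, and nothing in Table 5-1 says that it does.

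Its reach is limited to ofatumumab-treated patients who have stopped drug, remain depleted, and are considered for a live vaccine. The documents give neither the number of such patients nor a definition of exposure, so no count or duration is claimed. The related information gap is narrow: no stated route to B-cell status for vaccination purposes while counts are blinded, and no demonstration of repletion for those who began another therapy before 36 weeks. Hypothesis testing, power and the primary analysis are not affected. Which clinical rule is right is not judged here.

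**What to change.** Reconcile the Table 5-1 row and the 15.3 sentence to a single condition, worded identically in both, with its terms defined and a cross-reference each way. If the sponsor keeps a condition based on B-cells, add vaccination to the reasons for which the existing yes/no status in 5.6.2 may be requested, so that the investigator can learn whether the condition is met without seeing counts. The choice of condition, and of the definition behind it, belongs to the sponsor.

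The cost is one table row, one appendix sentence and, if needed, a wider scope for a request procedure that already exists. No new assessment, sample or analysis is required.

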5.5.9 Emergency breaking of assigned treatment code

Emergency code breaks must only be undertaken when it is required to in order to treat the patient safely. Most often, study treatment discontinuation and knowledge of the possible treatment assignments are sufficient to treat a study patient who presents with an emergency condition. Emergency treatment code breaks are performed using the IRT. When the Investigator contacts the system to break a treatment code for a patient, he/she must provide the requested patient identifying information and confirm the necessity to break the treatment code for the patient. The Investigator will then receive details of the investigational drug treatment for the specified patient and a fax or email confirming this information. The system will automatically inform the Sponsor monitor for the site and the Study Team that the code has been broken.

It is the Investigator's responsibility to ensure that there is a dependable procedure in place to allow access to the IRT at any time in case of emergency. The Investigator will provide:

- protocol number
- study drug name
- patient number

In addition, oral and written information to the patient must be provided on how to contact the Investigator's backup in cases of emergency, or when the Investigator is unavailable, to ensure that un-blinding can be performed at any time.

After an emergency treatment code break, the patient should discontinue study drug and will have their EOS visit as soon as possible ([Table 6-1](#)). Patients will be followed up for safety in the Safety FU period ([Table 6-2](#)).

